#### **7.3.3.8 Electrocardiogram**

A 12-lead ECG will be recorded at the time points specified in [Table 1](#). When timings of measurements coincide, ECGs should be performed before laboratory blood collection.

A central ECG reader will be used in this study. The eligibility of the subject is based on the assessment of the ECG by the investigator. If abnormal results are observed following assessment by the central reader, the investigator, in consultation with the appointed sponsor or contract research organization (CRO) medical monitor, reconfirms subject eligibility to continue.

### **7.3.3.9 Antidrug Antibodies**

Blood samples for measurement of antidrug antibodies (ADAs) and neutralizing antibodies (NABs) will be collected at the time points specified in [Table 1](#). Blood samples must be collected before the administration of investigational product at that visit.

### **7.3.3.10 Monitoring for Type I and Type III Immune Reactions**

Subjects will be educated on the signs and symptoms of hypersensitivity reactions and how to respond to them. In addition, subjects will be instructed to report hypersensitivity AEs to the investigator at the time of occurrence, and to seek immediate medical care if hypersensitivity develops. At each visit, the subject will be queried for adverse events of special interest (AESIs) related to hypersensitivity.

Subjects will be also instructed to report AEs such as serum sickness, vasculitis, Arthus reaction, and severe injection-related reactions to the investigator, and to seek immediate medical care if these events are severe in intensity.

Subjects who experience a hypersensitivity reaction or severe or serious injection-related reaction (eg, shortness of breath, wheezing, stridor, angioedema, life-threatening change in vital signs) should discontinue investigational product until the adjudication committee assess the case and finalize recommendation of permanent discontinuation or rechallenge with investigational product.

Subjects who experience an AE suggestive of the presence of circulating immune complexes formation (eg, fever, rash [including hives], arthralgia, myalgia, vasculitis, Arthus reaction, general ill feeling, itching, and swollen lymph nodes) will have the related AEs reviewed by the adjudication committee and if the AEs are assessed as related to formation of circulating of immune complexes and not related to underlying disease, blood samples will be collected and stored at the central laboratory. Tests will be performed as confirmatory of presence of circulating immune complexes at the request of the adjudication committee.

Further details of hypersensitivity reactions as AESIs are provided in [Section 8.1.3.1](#).

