**Table 1 Schedule of Assessments**

Study Week	Baseline a	Treatment												Follow-Up b		
	0	4	8	12	16	20	24	28	32	36	40	44	48	52/ET c	64 c	
Visit Number	1	2	3	4	5	6	7	8	9	10	11	12	13	14 (Pt 1) d	14 (Pt 2) d	15
Study Day	1	28	56	84	112	140	168	196	224	252	280	308	336		364	448
Visit Window	None	±10 days													±10 days	±10 days

s Mayo and PRO-UC assessments will be based on the subject's daily e-diary entries.

t The total Mayo score at Week 52/ET (Visit 14, Part 2) will be calculated based on the centrally read endoscopic subscore for the endoscopy performed at Week 52 (Visit 14, Part 1).

u PRO-UC daily e-diary will be available throughout the study. Subjects will be required to enter e-diary data daily. See Section 7.3.2.3 for further details. Compliance is assessed by site staff at each visit. The site staff will instruct the subject on the appropriate use of the e-diary, particularly when compliance is below 80% (eg, <8 out of 10 diary entries) when compared with the previous visit.

v All patient-reported questionnaires should be completed before completing any other visit assessments.

w Interactive response technology will be used for randomization and dispensation of study treatment.

x In a situation in which a subject is not able to visit the study site due to the COVID-19 public health emergency (or other similar pandemic), DTP investigational product administration options may be available, in accordance with local regulations (refer to DTP guidance document).

y At each visit, the subject will be assessed for the presence of Type I and Type III hypersensitivity reactions since the prior visit. If a suspected hypersensitivity reaction has occurred, the next dose of investigational product should be withheld if necessary until the precise etiology (investigational product related or not) has been determined. If a Type III reaction is suspected, appropriate samples for testing will be collected and stored until the adjudication committee determines whether testing is appropriate.

z Stool sample collection kit will be dispensed to the subject to take home at the visit prior to the visit at which testing will be done.

Note: See Section 7.3 for the order in which assessments should be performed. Timing of visits is relative to SHP647-303 baseline (Visit 1).

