Signs and symptoms of immune complex deposition typically have onset 1 to 3 weeks after exposure ([Warrington et al., 2018](#)) usually improving in 7 to 10 days, with full recovery in 2 to 4 weeks and may include fever, rash (including hives), arthralgia, myalgia, vasculitis, Arthus reaction, general ill feeling, itching, and swollen lymph nodes. Some of these findings, such as fever, rash, arthralgia, and myalgia are consistent with findings associated with IBD and may therefore be very difficult to assign to a particular etiology. When such a reaction is suspected,

samples for laboratory assessment will be obtained and stored. Tests will be performed if the diagnosis is confirmed and requested by the adjudication committee.

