#### 9.5 Planned Interim Analysis, Adaptive Design, Data Monitoring Committee, and Hypersensitivity Adjudication Committee

There is no planned interim analysis or adaptive design in this study.

An external DMC will be established to review the overall safety of the study subjects on an ongoing basis.

Until the time of unblinding, the DMC will be responsible for the ongoing monitoring of safety of subjects enrolled in the study according to the DMC charter. Recommendations made by the DMC to alter the conduct of the study or to amend the protocol will be forwarded to Shire for review and for a final decision. Shire or its designee will notify investigative sites and regulatory authorities as appropriate, of DMC recommendations (which may include summaries of aggregate analyses of endpoint events and of safety data that are not endpoints).

Further details regarding the DMC can be found in the DMC charter, which will be available before the administration of investigational product to any subject. Analyses of the data for DMC review will be conducted according to the DMC charter and the DMC SAP. Because no formal hypothesis testing for safety assessments is planned, multiplicity concerns regarding repeated analyses are not applicable.

An external hypersensitivity adjudication committee will be established to review data from subjects who experience a suspected Type I or Type III hypersensitivity reaction in order to confirm the nature and etiology of the reaction, to determine whether testing should be performed on stored blood samples, and to finalize recommendations of permanent discontinuation or rechallenge with investigational product. Further details regarding the adjudication committee can be found in the adjudication charter.

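### Protocol 7.3.3.10 makes the immune-complex blood draw wait for the adjudication committee's causality judgement, while Table 1 footnote y, Protocol 8.1.3.1 and SAP Appendix 16.2 draw and store the sample at suspicion

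*Protocol*

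**What the plan says.** Protocol 7.3.3.10 covers subjects with an adverse event that suggests circulating immune complexes. They "will have the related AEs reviewed by the adjudication committee", and the next step is conditional: "if the AEs are assessed as related to formation of circulating of immune complexes and not related to underlying disease, blood samples will be collected". The samples are then stored centrally and tested if the committee asks.

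Three places give a different trigger:

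- Protocol Table 1 footnote y: "If a Type III reaction is suspected, appropriate samples for testing will be collected and stored until the adjudication committee determines whether testing is appropriate".
- Protocol 8.1.3.1, again starting from suspicion: "samples for laboratory assessment will be obtained and stored. Tests will be performed if the diagnosis is confirmed and requested by the adjudication committee".
- SAP Appendix 16.2 footnote y, which repeats the protocol footnote.

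Protocol 9.5 has the committee review suspected reactions and, among other tasks, "to determine whether testing should be performed on stored blood samples". This is compatible with an earlier draw but does not say when the draw happens.

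On the clinical course, 8.1.3.1 states: "Signs and symptoms of immune complex deposition typically have onset 1 to 3 weeks after exposure", "usually improving in 7 to 10 days, with full recovery in 2 to 4 weeks". It also says that several of the signs occur with inflammatory bowel disease itself and are hard to attribute. Committee turnaround is not stated; 9.5 refers to the adjudication charter for details.

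**The concern.** The passages disagree on what triggers the draw. In 7.3.3.10 it is a causality judgement by an external committee; elsewhere it is suspicion at the site. Two consequences follow if a site works from 7.3.3.10.

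First, the draw is later by the length of the committee's review, and the reaction is described as self-limiting over weeks. Second, an event judged unrelated, or attributed to underlying disease, leaves no sample at all. That judgement is the one 8.1.3.1 describes as very difficult, and under 7.3.3.10 it must be made before any blood is available. The second consequence does not depend on how fast the committee works.

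Hypersensitivity is the protocol's named adverse event of special interest, and the study has approximately 164 sites (Protocol 3.3). Sites following different sections could collect this evidence at different times, or not at all, for the same kind of event.

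**Working it through.** The plan gives no figure to reproduce. The check compares the order of steps and then does date arithmetic on the protocol's own symptom course.

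**Order of steps**

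| Place | Trigger for the draw | What waits for the committee |
|---|---|---|
| Protocol 7.3.3.10 | Event assessed as immune-complex related and not due to underlying disease | Collection and testing |
| Protocol Table 1, footnote y | Suspicion | Testing only |
| Protocol 8.1.3.1 | Suspicion | Testing only |
| SAP Appendix 16.2, footnote y | Suspicion | Testing only |
| Protocol 9.5 | Not stated | Testing of samples already stored |

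**Inputs for timing**, in days from symptom onset (8.1.3.1, taking its intervals as counted from onset):

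- Improvement: 7 to 10.
- Full recovery: 2 × 7 = 14 to 4 × 7 = 28.
- R, the lag from onset to report: 7.3.3.10 tells subjects to report when the event occurs, so R can be near 0. If the event is first raised at the next four-weekly visit, onset 7 to 21 days after a dose gives R = 28 − 21 = 7 to 28 − 7 = 21 (nominal visit days).
- L, the committee review time: not in the documents; shown over an assumed range of 0 to 42.

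**Formulas.** Under 7.3.3.10, draw day = R + L. Under collection at suspicion, draw day = R. The draw is after improvement in some cases if the day exceeds 7 and in all cases if it exceeds 10. It is after full recovery in some cases if the day exceeds 14 and in all cases if it exceeds 28. Here *all cases* means across the whole of the protocol's stated range.

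**Results under 7.3.3.10**

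| R | L | Draw day | After improvement | After full recovery |
|---|---|---|---|---|
| 0 | 7 | 7 | no | no |
| 0 | 10 | 10 | some | no |
| 0 | 14 | 14 | all | no |
| 0 | 21 | 21 | all | some |
| 0 | 28 | 28 | all | some |
| 0 | 42 | 42 | all | all |
| 7 | 0 | 7 | no | no |
| 7 | 7 | 14 | all | no |
| 7 | 28 | 35 | all | all |
| 21 | 0 | 21 | all | some |
| 21 | 10 | 31 | all | all |

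The rows with L = 0 are also the results under collection at suspicion. With prompt reporting that order samples at about day 0. With R = 21 even that order samples after improvement, so reconciling the text removes L but not R.

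**The case against.** The best defence is that sites are already told to draw at suspicion. The schedule of assessments says so, the SAP repeats it, and 7.3.3.10 itself points to 8.1.3.1 for further detail. Reporting should be quick, since events of special interest follow the 24-hour timeline for serious events (Protocol 8.1.3 and 8.2.2). Exposure is also limited: enrollment is final at 366, and under Amendment 3 each subject's next visit is Week 52/ET. These points reduce the practical weight but do not remove the conflict. The cross-reference sends the reader to an instruction that contradicts the one just read, and Table 1 keeps hypersensitivity monitoring running through the Week 64 follow-up visit.

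A reader might also infer more than the documents support:

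- *Late samples would test falsely negative.* Protocol 8.1.3.1 gives the course of signs and symptoms, not how long immune complexes stay detectable, and no assay or detection window is given.
- *Type III reactions would be undercounted, and the SAP needs a rule for late samples.* SAP 7.1.1.1 summarizes events as adjudicated and has no rule by which a negative laboratory result removes one. Under 7.3.3.10 the causality judgement precedes the sample anyway.
- *Nearly all draws would come too late.* That follows only if a long review is assumed. With immediate reporting, up to 7 days of review still samples before improvement.
- *Section 9.5 orders collection at suspicion, or 7.3.3.10 leaves the committee nothing stored.* Section 9.5 does not state when blood is drawn, and 7.3.3.10 does store the samples it collects.

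**Conclusion.** The inconsistency is real, is in current text, and is more than missing detail: 7.3.3.10 conflicts with two other places in the protocol and one in the SAP on when blood is drawn. That conclusion needs no assumption beyond the natural reading that the assessment in 7.3.3.10 is the committee's.

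The established consequences are a delay equal to the review time and no sample for events judged unrelated. The size of the delay is unknown because the review time is not given. The sample could be taken after the episode: on the stated symptom course with immediate reporting, this becomes possible once review exceeds 14 days and holds in all cases beyond 28. What a late sample would show, and any effect on the count of adjudicated reactions, cannot be established from these documents.

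**What to change.** Reconcile the 7.3.3.10 sentence with Table 1 footnote y, 8.1.3.1, 9.5 and SAP Appendix 16.2 footnote y, so that all give one order of collection and committee review. Record the draw date relative to adverse event onset, so that anyone reading a test result can see where in the episode the sample fell.

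If the text is brought into line with collection at suspicion, the cost is one protocol sentence and one recorded date. It adds no procedure, because footnote y already requires the draw. The small downside is that some stored samples would never be tested. No change to the SAP's counting of hypersensitivity events is needed on this account.

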### 7.3.3.11 Evaluation of Increased Gastrointestinal Symptoms

When a subject experiences an increase in GI symptoms, which could be an exacerbation of disease, an infectious etiology must be evaluated including testing for *C. difficile* as described in [Appendix 4](#). If the subject has undergone or is undergoing a glucocorticoid taper, the glucocorticoid dose should be increased to the pre-taper dose; when clinically stable, the taper may begin again per [Table 3](#).

Subjects should be assessed for possible treatment failure no earlier than the Week 4 scheduled visit. If treatment failure is considered after infectious etiology has been ruled out or treated, and/or after increase in the glucocorticoid dose (if appropriate), then the procedures in [Section 4.5.1.1](#) should be followed.

In each case, the appropriate AE (eg, infection, exacerbation) should be recorded in the subject's source document.

### 7.3.4 Others

#### 7.3.4.1

[REDACTED]

[REDACTED]

- [REDACTED]
- [REDACTED]

[REDACTED]

[REDACTED]

### 7.3.5 Volume of Blood to Be Drawn from Each Subject

The volume of blood to be drawn from each subject is summarized in [Table 5](#).

**Table 5 Volume of Blood to Be Drawn from Each Subject**

Assessment	Sample Volume (mL)	Number of Samples	Total Volume (mL)
Hematology	2	5	10
Serum chemistry	4	5	20
FSH	2	1	2
ADA and NAb sampling	3	3	9
[REDACTED]			
[REDACTED]	2	3	6
Total mL			47

ADA=antidrug antibody; [REDACTED]; FSH=follicle-stimulating hormone; NAb=neutralizing antibody

The amount of blood to be drawn for each assessment is an estimate. The amount of blood to be drawn may vary according to the instructions provided by the manufacturer or laboratory for an individual assessment; however, the total volume drawn over the course of the study should be approximately 47 mL. When more than 1 blood assessment is to be done at the time point/period, if they require the same type of tube, the assessments may be combined.

## **8. ADVERSE AND SERIOUS ADVERSE EVENTS ASSESSMENT**

### **8.1 Definition of Adverse Events, Period of Observation, Recording of Adverse Events**

An AE is any untoward medical occurrence in a clinical investigation subject administered a pharmaceutical product and that does not necessarily have a causal relationship with this treatment. An AE can therefore be any unfavorable and unintended sign (including an abnormal laboratory finding), symptom, or disease temporally associated with the use of a medicinal (investigational) product, whether or not related to the medicinal (investigational) product (International Council for Harmonisation [ICH] Guidance E2A 1995).

All AEs are collected from the time the informed consent and/or assent is signed until the end of the defined safety follow-up period stated in Section 7.2.3. Where possible, a diagnosis rather than a list of symptoms should be recorded. Resolved AEs considered to be significant by the investigator that occurred in induction studies SHP647-301 or SHP647-302 will be captured as part of the SHP647-303 baseline medical history, while ongoing AEs from Studies SHP647-301 or SHP647-302 will be captured as AEs in SHP647-303 and followed throughout the SHP647-303 study. If a diagnosis has not been made, then each symptom should be listed individually. All AEs should be captured in the subject's source documents. In addition to untoward AEs, unexpected benefits outside the investigational product indication should also be captured in the subject's source document.

All AEs must be followed to closure (the subject's health has returned to his/her baseline status or all variables have returned to normal), regardless of whether the subject is still participating in the study. Closure indicates that an outcome is reached, stabilization achieved (the investigator does not expect any further improvement or worsening of the event), or the event is otherwise explained. When appropriate, medical tests and examinations are performed so that resolution of event(s) can be documented.

#### **8.1.1 Severity Categorization**

The severity of AEs must be recorded during the course of the event including the start and stop dates for each change in severity. An event that changes in severity should be captured as a new event. Worsening of pretreatment events, after initiation of investigational product, must be recorded as new AEs (for example, if a subject experiences mild intermittent dyspepsia before dosing of investigational product, but the dyspepsia becomes severe and more frequent after first dose of investigational product has been administered, a new AE of severe dyspepsia [with the appropriate date of onset] is recorded in the subject's source document).

The medical assessment of severity is determined by using the following definitions:

**Mild:** A type of AE that is usually transient and may require only minimal treatment or therapeutic intervention. The event does not generally interfere with usual activities of daily living.

**Moderate:** A type of AE that is usually alleviated with specific therapeutic intervention. The event interferes with usual activities of daily living, causing discomfort but poses no significant or permanent risk of harm to the research subject.

**Severe:** A type of AE that interrupts usual activities of daily living, or significantly affects clinical status, or may require intensive therapeutic intervention.

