## 9.9 Safety Analyses

All safety analyses will be performed using the safety set. Subjects will be analyzed according to the treatment they actually received.

Adverse events will be coded using the Medical Dictionary for Regulatory Activities.

Treatment-emergent AEs are defined as AEs with start dates at the time of or following the first exposure to investigational product in the SHP647-303 study. The number of events, incidence, and percentage of TEAEs will be calculated overall, by SOC, by preferred term, and by treatment group. Treatment-emergent AEs will be further summarized by severity and relationship to investigational product. Adverse events leading to withdrawal, SAEs, and deaths will be similarly summarized or listed. Adverse events of special interest will be summarized by treatment group.

Clinical laboratory tests, vital signs, and ECG findings will be summarized by treatment group and visit. Potentially clinically important findings will also be summarized or listed.

Antidrug antibody data will be summarized by treatment group and visit.

Further details of safety analyses will be described in the SAP.

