7.1 Adverse Events

Adverse events will be coded using MedDRA Version 19.1 2016.

Treatment-emergent AEs (TEAEs) are defined as AEs with start dates at the time of or following the first exposure to IP in the SHP647-303 study.

An overall summary of the number of subjects with TEAEs will be presented, including the number and percentage of subjects with any TEAEs, serious TEAEs, TEAEs related to IP, related serious AEs (SAEs), TEAEs leading to discontinuation of IP, TEAEs leading to study discontinuation, and TEAEs leading to death.

The number of events, incidence, and percentage of subjects reporting TEAEs will be presented by treatment group as listed in Appendix 16.6; by preferred term; by SOC and preferred term; and by SOC, preferred term, and maximum severity. Treatment-emergent AEs considered related to IP will also be summarized by SOC and preferred term. If more than one AE occurs with the same preferred term for the same subject, then the

subject will be counted only once for that preferred term using the most severe and most related occurrence for the summarization by severity and by relationship to IP.

The most common TEAEs (incidence $\geq 2\%$ in any treatment group) will be summarized by preferred term in descending frequency by treatment group as listed in Appendix 16.6.

Serious TEAEs, TEAEs leading to discontinuation of the study or study medication, and injection site AEs will be summarized by SOC, preferred term, and treatment group as defined in Appendix 16.6. Adverse events leading to withdrawal, serious AEs, and deaths will be similarly summarized or listed.

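### Protocol 8.1.1 does not limit new severity records to worsening and a TEAE is defined by start date alone, so a carried-over induction AE that steps down in severity can count as treatment-emergent

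*Protocol*

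**What the plan says.** Three rules act together.

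- **Carry-over (Protocol 8.1).** AEs not resolved at the end of induction stay in the data: "ongoing AEs from Studies SHP647-301 or SHP647-302 will be captured as AEs in SHP647-303 and followed throughout the SHP647-303 study".
- **Recording (Protocol 8.1.1).** Severity is recorded "including the start and stop dates for each change in severity". Then: "An event that changes in severity should be captured as a new event". The sentence after that deals with events that began before dosing: "Worsening of pretreatment events, after initiation of investigational product, must be recorded as new AEs". Its example is a mild event that becomes severe.
- **Classification (SAP 7.1).** TEAEs are "AEs with start dates at the time of or following the first exposure to IP in the SHP647-303 study". Protocol 9.9 and the Safety Analyses part of the synopsis use the same start-date rule. None of the three adds a condition on severity.

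SAP 7.1 then specifies the output: "The number of events, incidence, and percentage of subjects reporting TEAEs will be presented by treatment group". Where a subject has several AEs with one preferred term, SAP 7.1 counts the subject once, at the most severe and most related occurrence.

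**The concern.** A start-date definition of treatment emergence works if a record dated after first dose always means that something new or worse has happened. Protocol 8.1.1 does not guarantee that. If a fall in severity also opens a new record, the record of a pre-existing event getting better carries a post-dose start date and passes the TEAE test.

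This matters more here than in a trial that starts from a clean baseline. Every subject enters from a 12-week induction study, and ongoing AEs are brought across by design. The affected outputs are the number of TEAEs and the percentage of subjects with TEAEs, overall and by preferred term.

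**Working it through.** The documents state no figure for this, so the check is a trace of cases through Protocol 8.1, 8.1.1 and 9.9 and SAP 7.1. I assume that a carried-over AE keeps its induction onset date, which the documents do not state, and that 8.1.1 is applied as its unqualified sentence reads.

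| Course of the AE | Records starting after first SHP647-303 dose | TEAE events counted | Appropriate count |
|---|---|---|---|
| Carried over, severity unchanged | none | 0 | 0 |
| Carried over, resolves | none | 0 | 0 |
| Carried over, mild to severe | severe | 1 | 1 |
| Carried over, moderate to mild | mild | 1 | 0 |
| Carried over, severe to moderate to mild | moderate, mild | 2 | 0 |
| On-study onset, severe to moderate to mild | severe, moderate, mild | 3 | 1 |

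Only a change of severity category without resolution triggers the problem. Improvement within a category, or resolution, opens no new record.

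**Does anything remove the extra record?**

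- The once-per-preferred-term rule in SAP 7.1 does not. In the moderate-to-mild case the moderate record predates the first dose and is not a TEAE. The mild record is the only one left, and it is counted. The rule also works on subjects, not on the number of events.
- SAP 12.5 concerns repeated assessments of safety parameters. SAP 12.6.4 to 12.6.6 concern missing AE dates, severity and relationship. None links successive severity records of one event.

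**Subject incidence.** A step-down record adds a subject to the any-TEAE row only if that subject has no genuine TEAE at all. It adds a subject to a preferred-term row only if there is no genuine TEAE of that term.

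**How sensitive are the tables?** The number of such records is unknown, but group sizes can be projected. This assumes that the 366 enrolled subjects split as the 696 planned did (592 from active induction, 104 from placebo induction), with 1:1 and 2:2:1 allocation.

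- From active induction: 366 × 592/696 = 311.3; divided by 4 = 77.8 per sequence.
- From placebo induction: 366 × 104/696 = 54.7; two fifths = 21.9 for each dose, one fifth = 10.9 for placebo.
- By maintenance treatment: 77.8 + 21.9 = 99.7 for each dose; 2 × 77.8 + 10.9 = 166.5, or about 167, for placebo.

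SAP Section 7 makes the display by maintenance treatment primary (groups of about 100, 100 and 167) and the display by treatment sequence secondary. SAP 7.1 lists common TEAEs at an incidence of 2% or more in any group. In the primary display 2/100 = 2.0% reaches that line in a dose group and 4/167 = 2.4% does so in placebo. In the secondary display 2/78 = 2.6% and 1/22 = 4.5% do so. A few step-down records could therefore bring a term into that table. This describes the table's sensitivity and does not estimate how often it would happen.

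**The case against.** The strongest reply is that Protocol 8.1.1 has a specific rule for events that predate dosing, and that rule mentions only worsening. If the general sentence already turned every change into a new AE, the specific one would be redundant. On that reading carried-over AEs open a new record only when they worsen, and the start-date test does its job. This is a reasonable reading, and it means that a reader should not infer that the protocol plainly orders improvements of induction AEs to be entered as new events. But the sentence does not exempt improvement, and the one before it has no limit of direction. Sites could record either way. The reply also does nothing for events that begin on study.

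Other points stand in part:

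- Splitting an on-study event by severity is a stated recording convention, and counting it as one event is a reporting choice. The choice should still be made explicit, because the number of events is tabulated.
- Later step-downs of an on-study event do not alter subject counts by maximum severity. Under Protocol 8.2.5 an SAE starts when serious criteria are met, so a step-down alone does not create a new SAE.
- SAP Section 1 places output specifications in a separate document, which I have not seen and which may link records. Neither the protocol nor the SAP says that it does.

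A reader might also infer bias against ontamalimab, on the argument that symptoms settle more often on drug and so produce more improvement records. The documents do not support that. The rule is the same in every arm, no improvement rates are given, and Protocol 8.1.5 keeps ordinary symptoms of the disease out of the AE data unless they worsen significantly.

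**Conclusion.** The gap is real but limited. On the plain text, a carried-over AE that drops a severity category without resolving after the first maintenance dose counts as a TEAE, and an on-study AE that steps down adds to the number of events. No other rule in either document removes these records. The result is inflated event counts, and inflated subject incidence among subjects without a genuine TEAE, overall or of that term. If the extra records fall equally across arms, they dilute contrasts; a difference between arms would need different step-down rates and is not shown.

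The size cannot be derived. A reader might multiply the share of subjects entering with an ongoing AE by the share of those AEs that step down. Assumed values of 10 to 30% and 20 to 40% would give 0.10 × 0.20 = 2% to 0.30 × 0.40 = 12%. Neither share is in the documents, and the product is only a ceiling, because it ignores subjects who have a genuine TEAE anyway. It should not be quoted as an expected rate.

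The conclusion rests on the unqualified reading of 8.1.1 and on carried-over AEs keeping their induction onset dates. Under the narrower reading of 8.1.1, only the on-study event counts are affected. The plan should settle which reading applies.

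**What to change.** In SAP 7.1:

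1. Define a TEAE as an AE with first onset on or after the first SHP647-303 dose, or one whose severity increases after that dose relative to its pre-dose level.
2. State that a record continuing an earlier event at lower severity is neither a TEAE nor a separate event in event counts.
3. Identify a continuation by the same reported event and contiguous dates, and confirm it in data review. Matching on preferred term and contiguous dates alone could merge separate events.

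Align Protocol 9.9 and the synopsis, which carry the same definition, or list the change in SAP Section 14. Make the change before unblinding, when Protocol 9.4 requires the SAP to be final.

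The cost is SAP wording, one added AE-dataset derivation with a review step, and slightly lower event counts. No new data are needed, because Protocol 8.1.1 already requires the severities and their dates.
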